5.6 Participant Timeline

Table 1. Schedule of enrolment, interventions, and assessments.

	Pre-Surgery						P	Post-Surgery		Post randomisation	
Visit	Screening (Diagnosis)	Baseline	Randomisation - 4 weeks to surgery	Pre- surgery -4 to -3 weeks	Pre- surgery ≤ 7 days		Post- surgery discharge ~ 5-7 days	Post- surgery 30 days ¹	Post- surgery 6 weeks	6 month follow up visit ²	12 month follow up visit ²
Consent	Х									•	•
Eligibility	Х										
Demographics		Х									
Medical history		Х									
Hb result and document treatment for anaemia.		Х			Х						
Tumour histological stage								Χ			
СРЕТ		Х			Х						
SF36 Questionnaire		Х						Χ		X	Х
EQ-5D-5L Questionnaire		Х						Χ		X	Х
Hospital Anxiety and Depression Scale		Х				Surgery				X	Х
Self-Efficacy for Exercise Scale		Х				ırg				Х	Х
Behavioural Regulation in Exercise Questionnaire (BREQ-3)		Х				Sı				Х	Х
Exercise Identity Scale (EIS)		Х								Х	Х
Godin Leisure Time Exercise Questionnaire (modified)		Х								Х	Х
Resource Use questionnaire		Х								Χ	Х
Grip Strength		Х			Х			Χ		X	X
Full blood count and liver function tests ³		Х									
CT scans (staging/cancer surveillance) ³		Х								X	X
Randomise to Intervention			X								
Exercise Intervention (or TAU Arm C)									-		\longrightarrow
Record Adverse Events where applicable					\longmapsto		—				\longrightarrow
Record POMs in eCRF								\longrightarrow			
POM Clavien–Dindo Classification							Х	Х			
Blinded assessment of fitness for discharge							Χ				
Review of adherence to exercise interventions (if applicable)					Х					Х	Х

¹ The 30 Days post-surgery visits may take place within -3 days and +7 days of the schedule.

² The 6 and 12 Month follow-up visits should take place within ±6 weeks of the schedule

³ Results/images of FBC, LFTs and CT scans taken during standard care assessments uploaded onto eCRF for sub-study analyses

5.6.1 Patient Assessments

5.6.1.1 Screening visit

Written informed consent to enter and be randomised into the trial must be obtained from participants, after explanation of the aims, methods, benefits and potential hazards of the trial and **BEFORE** any trial-specific procedures are performed. The only procedures that may be performed in advance of written informed consent being obtained are those that would be performed on all patients in the same situation as usual standard of care.

If the PI or referring Co-I considers from a patient's medical notes that they may be eligible for the trial, the patient information sheet should be handed to the patient and they should be given adequate time to consider whether they wish to consent. This process must take place after diagnosis and once a decision to perform curative colorectal surgery has been reached, but should allow 3-4 weeks prior to surgery for the pre-surgery interventions to take place. If the patient is undergoing neo-adjuvant chemoradiotherapy, the treatment should be carried out before the patient is recruited to the study. If following the chemoradiotherapy clinical management plan is to proceed to a curative resection, the patient should then be approached for recruitment and randomisation to the study.

5.6.1.2 Baseline visit

Once the participant has given written informed consent, an initial CPET* should be performed.

If the participant is undergoing rectal cancer long course chemo-radiotherapy, this should be carried out before the baseline assessments.

All participants should have the following questions/questionnaires asked/administered; Quality of Life Questionnaires SF36 and EQ-5D-5L, Behavioural Regulation in Exercise Questionnaire (BREQ-3), Exercise Identity Scale (EIS), The Hospital Anxiety and Depression Scale, Self -Efficacy for Exercise Scale, modified version of Godin Leisure Time Exercise Questionnaire and Resource Use Questionnaire. Grip Strength should be measured using a standard digital grip strength dynamometer.

5.6.1.3 Randomisation

When the results of the CPET* are recorded and all baseline assessments have been completed, the option to randomise the participant will be available to the trial team. The participant should be randomised and this will decide the intervention they receive.

*Every effort should be made to ensure CPET data can be collected on each patient, but, if due to resource constraints or other exceptional circumstances, this would mean excluding a patient from the study, the patient may be randomised without CPET data. If a post-randomisation (within 7 days) baseline CPET is feasible prior to the start of the exercise intervention, the test should be completed and the results entered onto the eCRF at the baseline time point.

5.6.1.4 CPET guidance

For the purposes of this study, cardiopulmonary exercise tests should be completed as per standard local processes and procedures. However, the results should be uploaded onto the eCRF in breath-by-breath and/or 30 second average formats where possible.

If CPETs are carried out as part of standard care pre-surgical assessments, the results may be used for the baseline time point provided they are within 28 days of randomisation.

5.6.1.5 Pre-surgery treatment phase

Participants randomised to Arm A will receive:

Initial 45 minute exercise counselling session incorporating behaviour modification techniques, with the aim of raising awareness about the potential benefits of exercise and consequences of inactivity, decisional balance (positive/negative experiences of exercise, exercise preferences and overcoming fears about exercise, etc.), goal setting, self-regulation, safe physical exertion and practical advice for exercise. Patients will then be offered three sessions per week of aerobic interval exercise on a cycle ergometer over 3-4 weeks prior to their procedure to achieve up to 12 sessions. Patients are not required to attend a set minimum number of sessions but should be encouraged to attend as many pre-operative supervised exercise sessions as possible.

Each session will comprise 6 x 5 minute repetitions at 60-80% of heart rate reserve (~60-80% peak VO2; Borg RPE Scale 13-15 (Borg 1970), with 2.5 minute rest intervals. Heart rate, clinical signs, blood pressure and perceived exertion (via Borg RPE Scale) will be recorded regularly throughout exercise. The programme will be progressed as the patient becomes accustomed to exercise, by increasing the number of intervals to a maximum of 6 and /or adding further load to the cycle ergometer flywheel. Patients will receive instructions on how to complete an exercise diary for recording each exercise session (e.g. exercise modality, duration, intensity) and will be given a pedometer to record daily step counts.

There will also be 2 home-based resistance exercise sessions per week, using Thera-bands and body resistance, in accordance with current guidelines.

These sessions will be delivered by a member of the Trial Intervention Team who has had trial specific training to deliver these interventions consistently to all Arm A participants. Adherence to the exercise programme should be recorded in the eCRF, from pedometer data, patient participation/attendance and patient completed exercise diary. This is in addition to all other treatment as usual, offered prior to curative colorectal cancer surgery.

Participants randomised to Arm B will receive:

Initial 45 minute exercise counselling session incorporating behaviour modification techniques, with the aim of raising awareness about the potential benefits of exercise and consequences of inactivity, decisional balance (positive/negative experiences of exercise, exercise preferences and overcoming fears about exercise, etc.), goal setting, self-regulation, safe physical exertion and practical advice for exercise. This will be followed by a home exercise programme, aimed at achieving a minimum of 150 minutes of moderate intensity aerobic exercise per week (brisk walking/jogging/cycling/swimming, etc.), measured at 13-15 on the Borg RPE Scale (Borg 1970), and two sessions of resistance exercise (using Thera-bands and body weight, according to current guidelines). Exercise programmes will be tailored to each patient, taking previous level of activity, mobility and any barriers to exercise into consideration. Patients will also receive instructions on how to complete an exercise diary for recording each exercise session (e.g. exercise modality, duration, intensity) and will be given a pedometer to record daily step counts. Patients will receive weekly 15 minute telephone support from a member of the Trial Intervention Team to encourage compliance with the exercise programme.

These telephone calls will be made by a member of the Trial Intervention Team who has had trial specific training to deliver the intervention consistently to all Arm B participants. Adherence to the exercise programme will be recorded in the eCRF from pedometer data and patient completed exercise diaries. This is in addition to all other treatment as usual, offered prior to curative colorectal cancer surgery.

Participants randomised to Arm C will receive:

Other than the patient information leaflet, no other information relating to pre-operative exercise will be offered other than what is offered as part of standard care within the Trust. They will receive all other treatment as usual, offered prior to curative colorectal cancer surgery.

5.6.1.6 Within ≤7 days pre-surgery

All participants (all arms) must have their second CPET within 7 days prior to their curative surgery taking place, grip strength should be measured at the same time. If due to resource constraints or other exceptional circumstances, a second CPET is not possible, the patient can continue with data from one (or no) CPETs.

In the event that a patients surgery is postponed, the patient should continue with the exercise intervention, if randomised to an intervention arm, and proceed to surgery following rescheduling by the local clinical team.

5.6.1.7 Surgery

Surgery and after care to follow treatment as usual, with no further study interventions until 6 weeks post-surgery. All POMs and length of hospital stay to be recorded in patient notes and ultimately captured in the eCRF.

5.6.1.8 Post-surgery discharge

POM Clavien-Dindo Classification to be recorded from surgery completion to point of discharge. Fitness for discharge to be assessed by clinical team blinded to treatment intervention.

5.6.1.9 30 day post-surgery visit

30 day post-operative morbidity (Clavien-Dindo Classification) to be recorded from review of patient notes, from the date of discharge to the 30 days post-surgery, SF-36 and EQ-5D-5L questionnaires to be completed and grip strength (measured using a standard digital grip strength dynamometer) recorded. This visit may take within -3 days and +7 days of the schedule.

Post-operative morbidities re-experienced or worsened from the post-surgery inpatient stay should be re-recorded at the 30 day time point. Otherwise the recording of post-operative complications should not be duplicated.

5.6.1.10 6 week post-surgery to 12 month post-randomisation treatment phase

If a patient's return to exercise/usual activities is delayed due to post-operative complications, they may continue in the study and re-commence the exercise intervention once they are able. The protocol treatment interruption should be noted in the eCRF.

Participants randomised to Arm A will receive:

Information on the location of local exercise facilities and physical activity schemes in their local communities. Patients will be encouraged to comply with current physical activity recommendations of completing 150 minutes of moderate intensity aerobic exercise per week (e.g. brisk walking, cycling etc.), measured at 13-15 on the Borg RPE Scale (Borg 1970), and two sessions of resistance exercise per week.

Patients will also be offered supervised "booster" exercise sessions, approximately monthly until 12 months post-randomisation.

Each session will comprise 6 x 5 minute repetitions at 60-80% of heart rate reserve ($^{\circ}$ 60-80% peak VO₂; Borg RPE Scale 13-15 (Borg 1970) with 2.5 minute rest intervals. There will also be 2 home-based resistance exercise sessions per week.

These sessions will be delivered by a member of the Trial Intervention Team who has had trial specific training to deliver these interventions consistently to all Arm A participants.

Adherence to the exercise programme will be recorded in the eCRF from pedometer data, patient participation/attendance and patient completed exercise diaries. All exercise intervention AEs will continue to be recorded.

This intervention is in addition to all other treatment as usual, offered post-curative colorectal cancer surgery.

Participants randomised to Arm B will receive:

Information on local exercise facilities and will be encouraged to engage in weekly self-directed exercise of 150 minutes of moderate intensity aerobic exercise per week (e.g. brisk walking, cycling etc.), measured at 13-15 on the Borg RPE Scale (Borg 1970), and two sessions of resistance exercise.

Patients will receive a 15 minute telephone contact support session each month with a member of the Trial Intervention Team, until 12 months post-randomisation. During each telephone support session, exercise progress will be reviewed with an opportunity for participants to discuss any issues. The Intervention Team will reinforce cognitive—behavioural strategies and ensure exercise diaries are being kept up-to-date and properly completed. These telephone calls will be made by a member of the Trial Intervention Team who has had trial specific training to deliver these interventions consistently to all Arm B participants.

Adherence to the exercise programme will be recorded in the eCRF from pedometer data and patient completed exercise diaries. All exercise intervention AEs will continue to be recorded.

This intervention is in addition to all other treatment as usual, offered post-curative colorectal cancer surgery.

Participants randomised to Arm C will receive:

No other information relating to post-operative exercise will be offered outside of current practice for the site. All other treatment as usual will be offered post-curative colorectal cancer surgery.

5.6.1.11 6 and 12 month post-randomisation follow-ups

All participants will be asked to complete questionnaires, these may be sent by post or online ahead of routine clinic visits at 6 and 12 months post-randomisation (patients to bring completed postal questionnaires with them to their visit and may request assistance if required at the visit). The following questionnaires will be administered; Quality of Life Questionnaires SF36 and EQ-5D-5L, Hospital Anxiety and Depression Scale, Self -Efficacy for Exercise Scale (qualitative assessment at 6 months), Behavioural Regulation in Exercise Questionnaire (BREQ-3), Exercise Identity Scale (EIS), modified Godin Leisure Time Exercise Questionnaire and Health Resource Use. Grip Strength (measured using a standard digital grip strength dynamometer) will be recorded, this will need to be completed at a clinic visit and sites will aim to coincide this with a routine visit at 6 and 12 months post-randomisation (± 6 weeks of schedule).

5.6.2 Early Stopping of Follow-up

If a participant chooses to discontinue their trial treatment, they should continue to be followed up as closely as possible to the follow-up schedule defined in the protocol, providing they are willing. They should be encouraged and facilitated not to leave the whole trial, even though they're no longer participating in the exercise intervention. If, however, the participant exercises the view that they no longer wish to be followed up either, this view must be respected and the participant withdrawn from the trial. NCTU should be informed of the withdrawal in writing via email and completing the relevant pages on the eCRF. Anonymised data already collected will be kept and included in analyses according to the intention-to-treat principle for all participants who stop follow up early. All identifiable data will be removed.

Participants who stop trial follow-up early will not be replaced.

5.6.3 Participant Transfers

If a participant moves from the area making continued follow up at their consenting site inappropriate, every effort should be made for them to be followed at another participating trial site. Written consent should be taken at the new site and then a copy of the participant's eCRF should be provided to the new centre. Responsibility for the participant remains with the original consenting site until the new consent process is complete.

5.6.4 Loss to Follow-up

Contact details will be stored in the patient records and usual hospital procedures will be used to contact the patient about follow up visits. If this is without success, the patient will be recorded as lost to follow up. Number of patients where this has occurred will be monitored by the TMG.

5.6.5 Trial Closure

The end of the trial is defined as 12 months after the last patient's randomisation to the trial.

5.7 Sample Size

An overall sample of 1146 patients (randomised 1:1:1) provides 90% power.

Post-operative complications are evident in 55% of patients by day 30 in patients receiving standard care. To detect a 25% reduction (relative risk 0.75) between standard care and each of the exercise groups (90% power, alpha 2.5%) 343 patients are required in each arm, giving 1029, 10% attrition rate - Total 1146. Average SF 36 score at 1 year is 52 SD 10.To detect a 3 unit difference between standard

care and each of the exercise groups (90% Power, alpha 2.5%) requires 276 in each arm, 3 arms 828, 20% attrition rate. Total 1035.

5.8 Recruitment and Retention

5.8.1 Recruitment

Recruitment will be organised on a regional basis with the support of NIHR LCRNs. It is anticipated the identified trial sites will between them recruit 1146 patients over the trial period agreed with the funder and all other relevant parties.

Clinicians working in the coloproctology units identified for the trial will be asked to identify potential patients. They will make an assessment of the patient's eligibility to join the trial before referring/providing patient information to prospective patients.

One of the stop/go criteria of the internal pilot study is to assess recruitment and retention after recruitment month 12 (trial month 18).

Following patient consent and recruitment, the Research Nurse will send the participant's GP a letter to inform him/her of their patient's participation in the study.

5.8.1.1 Recruitment to process evaluation

Pre-trial patients and staff: Patients and staff will be invited by a member of the research team to consent to allowing a researcher to observe pre- and post-operative consultations. Patients consenting to participate will not be randomised and will not be included in the main trial.

Main trial patients and staff: Patients and staff consenting to participate in the main trial will be given the additional option to participate in the process evaluation and offered this during recruitment to the main trial. Patients and staff will have the option of consenting to both the observations and interviews, or to only one or other of these components. Patients consenting to or interested in participating in the process evaluation will be approached by the local research team or research associate about being observed and/or for a future interview post-completion of the study.

5.8.2 Retention

Adherence to the treatment arms:

In order to be successful patients will need to adhere to the treatment arm. A pre-trial feasibility study confirmed that 90% of patients adhered to the prescribed pre-operative exercise training. An attrition rate of 10% has been included in the power calculation for the short-term primary outcome: 30-day complication. An attrition rate of 20% has been used for long-term primary outcome in keeping with other exercise intervention studies performed previously by members of the research team.

The pre-trial feasibility work included a patient perspective, which concluded that the intensity and duration of the aerobic exercise sessions were acceptable to the majority of patients. This is supported by the literature (Mazurek et al., 2014, Statts, 2002, Bartlett et al., 2011)

5.9 Assignment of Intervention

5.9.1 Allocation

Randomisation to treatment arm will take place after the baseline CPET (see Patient Assessments section 5.6.1) and all baseline assessments have been completed.

5.9.1.1 Sequence generation

Eligible, consented participants will be randomised on a 1:1:1 basis to one of three trial arms using a web based randomisation process. The randomisation scheme will be generated by the NCTU data manager and notified by email to the study team. Allocation will be stratified by centre using permuted block randomisation with randomly varying block sizes.

5.9.1.2 Allocation concealment mechanism

The allocation is computer generated so will not be known prior to the participant being randomised. The patient will be allocated a participant number at time of consent. When the results of the baseline CPET have been obtained, and all other pre-designated questions completed in the eCRF, the research staff will then have access to the randomisation process for that participant. (See also special circumstances for CPET collection in section 5.6.1.3). The treatment allocation will be revealed and linked to that participant number. Allocation is concealed prior to randomisation to prevent treatment bias.

5.9.2 Blinding

Blinding is not applicable to the delivery of the intervention in this trial.

Post-operative morbidities are recorded in the patient notes as part of standard care procedures during the initial surgical admission and for any subsequent admissions experienced. CPETs will be performed by local Trust staff who conduct these assessments part of their standard care.

Both the clinical team(s) responsible for the initial surgical and any subsequent admissions and the CPET team are independent of the study and will therefore be blinded to treatment arm allocation. Local study staff will review patient notes and enter details of any post-operative complications, in accordance with the Clavien-Dindo classification method, and upload CPET results onto the eCRF.

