	1. Contra-indications to exercise (e.g. lower limb
	amputation without prosthesis, bone, joint or
	muscle problem which may be exacerbated by
	exercise, chronic lung disease causing desaturation
	with exercise or shortness of breath at rest, severe
	psychiatric health problems)
	2. Cardiovascular contra-indications (e.g. unstable
	angina, acute left ventricular failure, uncontrolled
	cardiac arrhythmias, uncontrolled hypertension,
	cardiac event in the previous 6 weeks, cerebral
	vascular disease resulting in transient ischaemic
	attacks)
	3. Participation in other treatment trials, where this
	has not been agreed in advance with both trial
	teams.
Study Type	A multi-centre, single blind (assessors only), 3-arm
	randomised controlled trial recruiting cancer patients
	awaiting curative colorectal cancer surgery from colorectal
Data of First Foundation	units in the UK and Ireland
Date of First Enrolment Target Sample Size	1 November 2016 1146 patients
Primary Outcome(s)	Two primary outcomes will be used:
Trimary Gateome(s)	Two primary outcomes will be used.
	Short term outcome:
	Morbidity for standard care versus hospital based and
	standard care versus home based exercise interventions
	(both exercise interventions are in addition to treatment as
	usual). Assessed by Clavien-Dindo classification of post-
	operative complications
	Measured 30 days post-operatively
	Long Term Outcome:
	Health-related quality of life at 12 months for standard care
	versus hospital based and standard versus home based
	exercise interventions. Assessed by the Medical Outcomes
	Study Short-Form Health Questionnaire (SF-36) 12 months
	post-randomisation.

Key Secondary Outcomes

The following secondary outcomes will be assessed for standard care versus hospital based and standard care versus home based exercise interventions:

Pre-operative outcomes

The following outcomes will evaluate response to the intervention in the pre-operative phase of the study only.

Outcome: Pre-operative change in cardiopulmonary exercise test (CPET).

Metric: Change in cardiopulmonary fitness variables, as measured using an incremental CPET between 4 weeks prior to surgery and shortly before surgery (e.g. peak VO2; anaerobic/ventilatory threshold; VE/VCO2; oxygen pulse).

Outcome: Pre-operative change in grip strength.

Metric: Change in grip strength as measured using a standard digital grip strength dynamometer

Post-operative outcomes:

Outcome: Length of hospital stay

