5.5 Outcomes

5.5.1 Primary Outcomes

Two primary outcomes will be used:

Short Term Outcome; 30-day morbidity

30-day morbidity will be assessed using the Clavien-Dindo classification of post-operative complications (Clavien et al. 2009), for standard care versus hospital based and standard care versus home based interventions. Data will be collected 30 days post-operation by the clinical team, who are blinded to treatment intervention, using a structured set of questions during the routine post-operative review.

Long Term Outcome; health related quality of life

Health-related quality of life will be assessed by the Medical Outcomes Study Health Questionnaire (SF-36) (Ware et al., 1992) (total score) at 12 months post-randomisation, for standard care versus hospital based and standard care versus home based interventions.

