Appendix 1: Clavien Dindo classification of Post-Operative Morbidities (POM)

Full Scale				
Grades	Definition			
Grade I:	Any deviation from the normal postoperative course without the need for pharmacological treatment or surgical, endoscopic and radiological interventions.			
	Allowed therapeutic regimens are: drugs as antiemetics, antipyretics, analgetics, diuretics and electrolytes and physiotherapy. This grade also includes wound infections opened at the bedside.			
Grade II:	Requiring pharmacological treatment with drugs other than such allowed for grade I complications. Blood transfusions and total parenteral nutrition are also included.			
Grade III:	Requiring surgical, endoscopic or radiological intervention			
Grade III-a:	intervention not under general anesthesia			
Grade III-b:	intervention under general anesthesia			
Grade IV:	Life-threatening complication (including CNS complications)‡ requiring IC/ICU-management			
Grade IV-a:	single organ dysfunction (including dialysis)			
Grade IV-b:	multi organ dysfunction			
Grade V:	Death of a patient			
Suffix 'd':	If the patients suffers from a complication at the time of discharge, the suffix "d" (for 'disability') is added to the respective grade of complication. This label indicates the need for a follow-up to fully evaluate the complication.

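### The protocol conflicts on who classifies the 30-day complications and does not claim blinding for the local study staff named in 5.9.2, so the assessor-blind claim is unsupported for the short-term primary outcome.

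*Protocol*

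**What the plan says.** Section 1.3 describes the trial as "single blind (assessors only" in its study-type entry. For the short-term primary outcome, section 5.5.1 states: "Data will be collected 30 days post-operation by the clinical team, who are blinded to treatment intervention, using a structured set of questions", at the routine post-operative review.

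Section 5.6.1.9, on the 30-day visit, describes another route: "30 day post-operative morbidity (Clavien-Dindo Classification) to be recorded from review of patient notes". It names no assessor and says nothing about blinding.

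Section 5.9.2 has the clinical teams write morbidities in the notes as standard care. Those teams and the CPET team "are independent of the study and will therefore be blinded to treatment arm allocation". The next step is given to others: "Local study staff will review patient notes and enter details of any post-operative complications, in accordance with the Clavien-Dindo classification method". The section makes no statement about whether these staff are blinded.

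Section 5.9.1.2 says that once baseline data are in, "the research staff will then have access to the randomisation process for that participant", and then: "The treatment allocation will be revealed and linked to that participant number".

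Section 5.10.4.2 analyses the outcome as any morbidity, present or absent. Appendix 1 opens Grade I with "Any deviation from the normal postoperative course without the need for pharmacological treatment".

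For morbidity at discharge, a secondary outcome, section 1.3 calls a combined clinical or research team blinded, while section 5.5.2 names only the clinical team.

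**The concern.** Patients and intervention staff cannot be blinded here, so protection of the 30-day outcome rests on the person who decides whether a complication occurred. That decision is a yes/no call with a low threshold. Under one section a blinded team makes it. Under another it is made by local study staff, for whom no blinding is claimed and whose colleagues, at least, see the allocation. If a classifier who knows the arm leaves out minor events a little more readily in exercise patients, the comparison shifts in favour of exercise and no analysis can recover the difference.

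The two routes may also capture different events. Section 5.9.2 refers to notes from the surgical admission and later admissions. Structured questions at a review could also pick up minor problems after discharge that led to no admission.

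**Working it through.** **Who classifies, section by section**

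| Section | Who | How | Blinding stated |
|---|---|---|---|
| 5.5.1 (30-day primary) | Clinical team | Structured questions at routine review | Yes |
| 5.6.1.9 (30-day visit) | Not named | Notes review | None |
| 5.9.2 (Blinding) | Local study staff | Notes review, then Clavien-Dindo | None for these staff |
| 1.3 (discharge morbidity) | Clinical or research team | Clavien-Dindo | Yes, for discharge only |
| 5.5.2 (discharge morbidity) | Clinical team | Clavien-Dindo | Yes, for discharge only |

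Section 5.9.2 derives blinding from independence of the study. Local study staff are not independent in that sense. Section 5.3.1.3 lets any trained member of the research team, registered nurses included, deliver the intervention. No section bars such a person from abstracting the outcome.

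**The plan's own figure (background)**

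Inputs from section 5.7: control rate 0.55, relative risk 0.75, alpha 2.5%, power 90%, 343 per arm, 10% attrition.

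- Exercise rate: 0.55 × 0.75 = 0.4125. Target difference: 0.55 − 0.4125 = 0.1375, or 13.75 points.
- The two-sided two-proportion formula at alpha 2.5% gives 326 per arm, or 340 with continuity correction, close to the stated 343.
- Attrition: 343 / 0.9 = 381.1, rounded up to 382; 382 × 3 = 1146, as stated.

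The sample size is not in question.

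**Illustration of what a classification bias would do**

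Assumptions, none of them from the documents: no true effect, 55% in both arms, two-sided test, and a spurious difference d that always favours exercise.

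- SE = √(2 × 0.55 × 0.45 / 343) = 0.0380. Critical value z = 2.2414.
- P(reject) = [1 − Φ(2.2414 − d/SE)] + Φ(−2.2414 − d/SE).

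| d (points) | d/SE | P(reject) | Share of 13.75 points | Share of exercise patients with a complication who must be recorded as having none (d/55) |
|---|---|---|---|---|
| 0 | 0 | 2.5% | 0% | 0% |
| 1 | 0.263 | 3.0% | 7.3% | 1.8% |
| 2 | 0.526 | 4.6% | 14.5% | 3.6% |
| 3 | 0.790 | 7.5% | 21.8% | 5.5% |
| 5 | 1.316 | 17.8% | 36.4% | 9.1% |

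The last column shows how much misclassification each row needs. Every patient counted there must have no other event that qualifies as morbidity.

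**The case against.** The strongest reply is that the source record is protected. The notes are written by clinical teams said to be independent and blinded. Grades II to V turn largely on something recorded there: a drug, a transfusion, a procedure, intensive care or death. An abstractor has little room with those. This stands, and it confines the main exposure to Grade I in patients with no higher-grade event. It does not remove the exposure, because one Grade I event is enough to count as any morbidity.

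A second reply points to section 1.3, where a clinical or research team is called blinded for discharge morbidity. It bears on the primary outcome: under section 5.6.1.9 the 30-day record runs from discharge and inpatient events are not entered again unless they recur or worsen, so the in-hospital part comes from the discharge grading. But the wording covers the discharge outcome only. It also fits poorly with section 5.9.1.2, where research staff run the randomisation, and with section 5.9.2.

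A reader might infer that the people who randomise are the people who grade, and that the outcome is therefore unblinded. The documents do not say so: 5.9.1.2 refers to research staff, 5.9.2 to local study staff, and nothing states that the same individuals do both. Nor does 5.6.1.9 assign grading to study staff. Only the possibility is supported.

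It is also fair to object to making 5.5.1 the only rule. Section 5.9.2 rests the clinical team's blinding on its independence of the study. Asking that team to complete trial questions weakens this basis, and a conversation lets patients disclose their arm. This stands, and is why the fix offers two routes.

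**Conclusion.** The inconsistency is real and concerns a primary outcome. Sections 5.5.1, 5.6.1.9 and 5.9.2 do not agree on who assigns the 30-day classification or how, and no blinding is claimed for the staff named in 5.9.2. The outcome may be classified with knowledge of the arm, so the assessor-blind description is not supported for it.

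The size of any bias is unknown. The rise from 2.5% to between 3.0% and 17.8% is what assumed differences of 1 to 5 points would produce if every error favoured exercise. A reader might take the upper figure as this trial's error rate, but no section supports any particular value. The point should be corrected; it does not show that the outcome has been biased.

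**What to change.** Reconcile 5.5.1, 5.6.1.9, 5.9.2 and the discharge-morbidity wording in 1.3 into one rule, applied alike in all arms. Either route would do:

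1. The blinded clinical team assigns the classification and study staff only transcribe it.
2. Study staff enter the recorded event and the treatment given for it. Presence and grade are then derived from those fields by a fixed rule with the arm masked.

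Under both, staff who randomised the patient or delivered the intervention to that patient do not abstract the outcome. The protocol should name the person who classifies and state that person's blinding status. If patients already graded were classified by unblinded staff, report this and limit the assessor-blind claim accordingly.

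The cost is protocol and eCRF wording, some site coordination, and a change of procedure part-way through recruitment.
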